
(with past history of: hysterectomy, tubal ligation, infertility, menopause more than 1 year).
 
or
 
 – men with preserved reproductive function who use barrier contraceptives, as well as men with infertility or vasectomy in the past medical history. 
Non-inclusion criteria:
 
 1. Hypersensitivity to favipiravir and/or other components of the study drug. 2. Impossibility of CT procedure (for example, gypsum dressing or metal structures in the field of imaging). 3. The need to use drugs from the list of prohibited therapy. 4. Need for treatment in the intensive care unit. 5. Impaired liver function (AST and/or ALT ≥ 2 UNL and/or total bilirubin ≥ 1.5 UNL) at the time of screening. 6. Impaired kidney function (creatinine clearance according to Cocroft-Gault formula less than 45 ml/min) at the time of screening. 7. Positive testing for HIV, syphilis, hepatitis B and/or C. 8. Chronic heart failure FC III-IV according to New York Heart Association (NYHA) functional classification. 9. Malabsorption syndrome or other clinically significant gastrointestinal disease that may affect absorption of the study drug (non-correctable vomiting, diarrhea, ulcerative colitis, and others). 10. Malignancies in the past medical history. 11. Alcohol, pharmacological and/or drug addiction in the past medical history and/or at the time of screening. 12. Schizophrenia, schizoaffective disorder, bipolar disorder, or other history of mental pathology or suspicion of their presence at the time of screening. 13. Severe, decompensated or unstable somatic diseases (any disease or condition that threaten the patient's life or impair the patient's prognosis, and also make it impossible for him/her to participate in the clinical study). 14. Any history data that the investigating physician believes could lead to complication in the interpretation of the study results or create an additional risk to the patient as a result of his/her participation in the study. 15. Patient's unwillingness or inability to comply with procedures of the Study Protocol (in the opinion of physician investigator). 16. Pregnant or nursing women or women planning pregnancy. 17. Participation in another clinical study for 3 months prior to inclusion in the study. 18. Other conditions that, according to the physician investigator, prevent the patient from being included in the study. 		

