Sponsor: PROMOMED RUS LLC, Russia	Separate study table relating to part of the dossier	(For use by national authorized bodies only)
Name of finished product: Areplivir, film-coated tablets	Volume: Pages:	
Active ingredient: Favipiravir		
Investigational medicinal product, dose and mode of administration, batch number: Investigational medicinal product: Areplivir, film coated tablets (PROMOMED RUS LLC, Russia), batch 010520 (expiry date 06.2022). Patients in Arm 1 take the investigational product Areplivir, film coated tablets: on Day 1st of treatment - 1600 mg (8 tablets) 2 times a day; on days 2-14 of treatment - 600 mg (3 tablets) 2 times a day. The drug is taken orally every 12 hours, swallowing whole tablet without chewing and washing down with a glass of water. The course of treatment is 14 days. The test drug is administered in hospital setting under supervision of a clinical investigator. The test drug is not handed over to the patient.		
Duration of the study: The total duration of the study for the patient is not more than 31 days, of which the screening period is not more than 2 days. Visits: Visit 0 (screening, not more than 2 days); Visit 1 (randomization, day 1)*; Visit 2 (day 5); Visit 3 (day 10); Visit 4 (day 15)**; Visit 5 (day 21±1)***; Visit 6 (study completion, day 28±1)***. * Visit 1 may coincide with Visit 0. ** If a patient is discharged from hospital at an earlier date, the visit will be conducted at the time of discharge (for Arm 2 patients). *** If a patient is discharged from hospital at an earlier date, then this patient does not need to visit the study site. Fatalities and serious adverse events (SAE) will be followed-up through telephone contact with the patient. Discharge of patients from a hospital is carried out in accordance with the local practice of the study site in compliance with the current sanitary and epidemiological regime.		
Efficacy criteria: The efficacy of therapy is assessed using the following endpoints: Primary efficacy criterion: 
 • Time (in days) to improvement in clinical status by categorical ordinal scale of clinical status improvement. • Rate of clinical status improvement by categorical ordinal scale of clinical status improvement by 2 or more categories at Visit 3. Secondary efficacy criteria:		

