
Certified statistical software with validated algorithms is used to perform statistical analyses and to ensure proper documenting (StatSoft Statistica 10.0., IBM SPSS Statistics 22).
 
Descriptive statistics are provided for all efficacy and safety indicators collected during the study. Continuous (quantitative) data are presented using the number of observations, arithmetic mean value, confidence interval (CI) 95% for mean, standard (rms) deviation, median, interquartile span (25th and 75th centiles), minimum and maximum.
 
Ordinal, categorical and qualitative data are presented as absolute frequencies (number of observations), relative frequencies (percent) and 95% CI (unless otherwise stated).
 
The check for normality of distribution is carried out by one of the generally accepted methods (Shapiro-Wilk test, Kolmogorov-Smirnov test). For non-Gaussian distributions, non-parametric methods will be used to compare efficacy and safety indicators.
 
Significance levels and confidence intervals are calculated as bilateral, the statistical significance of differences is two-sided by default and refers to significance level 0.05 (unless specified otherwise).
 
Analysis of demographics and other source data
 
Demographic data (age, sex) and baseline condition data are presented along with summaries in the form of absolute frequencies (number of observations), relative frequencies (percent), or using the arithmetic mean, confidence interval (CI) 95% for mean, standard deviation, median, interquartile span (25th and 75th centiles), minimum and maximum, depending on the type of variable.
 
To test the study group homogeneity hypothesis, at the baseline zero hypotheses (no differences between groups) are tested with Student's t-test (for interval measures with normal distribution in the study population), Mann-Whitney's test (for ordinary measures or for interval measures with distribution different from normal) or Fisher's exact test and χ^2 test (for qualitative indicators). If statistically significant differences between study arms are found, the magnitude of differences is estimated using confidence intervals.
 
Analysis of primary efficacy parameter
 
Primary efficacy endpoints:
 
One of the primary efficacy parameters is the time (in days) to improvement of patient's clinical status according to the categorical ordinal scale of clinical improvement.
 
 • Time (in days) to improvement in clinical status on a categorical ordinal scale of clinical improvement. 
To compare the primary efficacy indicator between arms, the Student's t-test for independent samples is used. If the necessary assumptions about the normality of distribution of this indicator are not met, the non-parametric Mann-Whitney test will be used. Also, the Kaplan-Meier technique and compilation survival tables can be used as descriptive methods for studying this efficiency parameter. Gehan-Wilcoxon test, Cox-Mentel test or Log-Rank test can be used to compare the time (in days) to improve the clinical status of the patient between the study groups.
		

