- Percentage of cases with non-invasive lung ventilation.
- Percentage of cases with mechanical lung ventilation.
- Incidence of fatal cases.
- Assessment of lung injury according to CT data at Visits 4, 5 and 6.**

* Virus elimination is defined as two negative laboratory tests for SARS-CoV-2 RNA obtained at intervals of 24 hours.

**An "empirical" visual scale will be used to estimate changes in lung involvement from CT data.

For the analysis of these parameters, an intergroup comparison of shares is used using a two-sided version of the **Fischer's exact test** (or a two-sided version of the χ^2 (chi-square) test, if all the expected values in the cells of the contingency table for this analysis are 5 or more).

The protocol also includes the following endpoint:

- Time (in days) to fever disappearance (body temperature < 37.2 ° C for 3 consecutive days

Sponsor: PROMOMED RUS LLC, Russia	Separate study table relating to part of the dossier	(For use by national authorized bodies only)
Name of finished product: Areplivir, film-coated tablets	Volume: Pages:	
Active ingredient: Favipiravir		

without antipyretic medication).

For the secondary efficacy parameter "time (in days) to fever disappearance (body temperature < 37.2 °C for 3 consecutive days without antipyretic drugs), a comparison between arms is made using the *Student's t-test* or the *Mann-Whitney test* (depending on the nature of the distribution of quantitative indicators). Also, *Kaplan-Meier technique* and the construction of *survival tables* can be used as descriptive methods of study. The *Gehan-Wilcoxon test, the Cox-Mentel test or the Log-Rank test* can be used to compare the time (in days) to the disappearance of fever in the study arms.

Analysis of secondary efficacy parameters is performed in the ITT population (main analysis), and in the PP population (additional analysis).

In case of developing acute respiratory distress syndrome and the need to switch patient to mechanical ventilation, the investigational drug is canceled, but the patient is not withdrawn from the study. Patients are under follow-up until Visit 6, the data are taken into account to assess efficacy in the ITT population.

Safety Analysis

Safety criteria

Safety assessment includes the following parameters:

- Total number of adverse events (AEs) stratified by severity and incidence;
- Incidence of adverse drug reactions;

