- Incidence of serious adverse events (SAEs) associated with the use of the study drug/standard therapy;
- Percentage of patients with at least one AE;
- Percentage of patients who discontinuation treatment due to AE.

Cross-group comparisons are performed for all safety indicators. The comparison of groups on frequency indicators is carried out using the *Fischer's exact test* or the χ^2 (chi-square) test, depending on the expected value in the cells of contingency table. For quantitative laboratory results, comparisons between groups at relevant visits are made using the *Student's t-test* or the *Mann-Whitney test* (depending on the nature of the distribution of quantitative indicators).

For analysis of all safety parameters the safety population was used.

In case of developing acute respiratory distress syndrome and the need to switch patient to mechanical ventilation, the investigational drug is canceled, but the patient is not withdrawn from the study. Patients are under follow-up until Visit 6, the data are taken into account to assess efficacy in the ITT population.

Interim analysis

In the first stage, 40 patients were included in each group (study arm). Given 40 patients in each of the study arms, the sensitivity of the study to confirm 15% superiority by incidence, supposing the expected response 80% in the test drug arm, will exceed 45%.

Sponsor: PROMOMED RUS LLC, Russia	Separate study table relating to part of the dossier	(For use by national authorized bodies only)
Name of finished product: Areplivir, film-coated tablets	Volume: Pages:	
Active ingredient: Favipiravir		

Two Independent Proportions (Null Case) Power Analysis									
Numeric Results of Tests Based on the Difference: P1 - P2									
H0: P1 - P2 ≥ 0. H1: P1 - P2 = D1 < 0. Test Statistic: Z test with pooled variance									
		Sample Size	Sample Size	Prop H1	Prop				
		Grp 1	Grp 2	Grp 1 or	Grp 2 or	Diff	Diff	Target	Actu
	Power	N1	N2	Trtmnt	Control	if H0	if H1	Alpha	Alpha
				P1	P2	D0	D1		
	0.4553	40	40	0.6500	0.8000	0.0000	-0.1500	0.0500	0.0500

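### Laboratory values are compared between arms only by a test at each visit; adding counts of patients beyond a limit, with intervals, is a cheap improvement

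*Combined protocol and SAP*

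**What the plan says.** All references are to the Combined protocol and SAP, section 2, Overview (Synopsis).

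- **Safety Analysis.** "For quantitative laboratory results, comparisons between groups at relevant visits are made using the" t-test or Mann-Whitney test, according to the distribution. For event-type measures, "The comparison of groups on frequency indicators is carried out using the" Fisher exact or chi-square test. The five safety criteria concern adverse events, adverse reactions, related serious events, patients with any event, and discontinuations. None is a laboratory category.
- **General methods of analysis.** "The check for normality of distribution is carried out by one of the generally accepted methods", with Shapiro-Wilk and Kolmogorov-Smirnov named, and then "For non-Gaussian distributions, non-parametric methods will be used to compare efficacy and safety indicators". For description, "Continuous (quantitative) data are presented using the number of observations, arithmetic mean value, confidence interval (CI) 95% for mean", followed by SD, median, quartiles, minimum and maximum. Categorical data get frequencies with a 95% interval.
- **Non-inclusion criteria 5 and 6.** Liver and kidney limits appear only as entry rules: "Impaired liver function (AST and/or ALT ≥ 2 UNL and/or total bilirubin ≥ 1.5 UNL) at the time of screening", and a creatinine clearance below 45 ml/min.
- **Analysis of primary efficacy parameter.** A Newcombe-Wilson interval for a difference in proportions is planned, but only for the response rate.
- **Duration of the study.** For Visit 4 (day 15), if discharge comes sooner, "the visit will be conducted at the time of discharge (for Arm 2 patients"). A patient already discharged need not attend Visits 5 and 6.

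**The concern.** Mann-Whitney compares ranks. If an affected patient already has the highest value, it makes no difference whether that value is 3 or 15 times the upper normal limit (UNL). A test of this kind responds to a shift in most patients and only weakly to harm in a few. Liver injury in a minority of treated patients would be harm of the second kind.

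The plan excludes patients with impaired liver or kidney function, so these organs are clearly of interest, and safety is one of the two study objectives. If harm is confined to a subset, a non-significant p-value at each visit is weak evidence of no difference. The stated outputs also do not tell a reader how many patients in each arm crossed a limit. The plan has no statistical stopping rule, so what is at stake is the reading of the safety results, not a decision to stop.

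**Working it through.** **Inputs.** From the plan: 100 per arm planned, 40 per arm in the interim report, two-sided 0.05. The plan states no power for laboratory safety; its power figures concern response rates, so there is none of its own to reproduce here. Assumed: the excess of affected patients in Arm 1, shown as a range.

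**1. Closed form for one visit.** Let shares p1 (Arm 1) and p2 (Arm 2) be affected, with affected values above all others and the unaffected distributed alike. Then

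P(X>Y) + ½P(tie) = ½·p1·p2 + p1(1−p2) + ½(1−p1)(1−p2) = 0.5 + e/2, where e = p1 − p2.

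SE = sqrt((2n+1)/(12n²)), which is sqrt(201/120000) = 0.0409 at n = 100 and sqrt(81/19200) = 0.0650 at n = 40.

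With d = (e/2)/SE, power = Φ(d − 1.96) + Φ(−d − 1.96). For e = 0.08 and n = 100, d = 0.04/0.0409 = 0.98 and power is 16.5%.

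| Excess (points) | 100 per arm | 40 per arm |
|---|---|---|
| 3 | 6.6% | 5.6% |
| 5 | 9.4% | 6.7% |
| 8 | 16.5% | 9.4% |
| 10 | 23.1% | 12.0% |
| 15 | 44.9% | 21.1% |

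Power reaches 50% at e = 2 × 1.96 × SE, which is 16.0 points at 100 per arm and 25.5 at 40. Simulation (20,000 trials) gave 15.9% to 16.5% at 8 points and 100 per arm.

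**2. What counts add at 100 per arm.** If the limit identifies every affected patient, Fisher power for an 8-point excess is 82% (8% v 0%), 68% (9% v 1%), 58% (10% v 2%) and 42% (13% v 5%). A more realistic ALT model lowers this. It assumes lognormal values, median 0.6 UNL, log-SD 0.35 to 0.55, and affected values multiplied by 4 to 10. For a single measurement:

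| Affected, Arm 1 v Arm 2 | Mann-Whitney | Fisher on ≥ 2 UNL |
|---|---|---|
| 8% v 0% | 16% | 50-74% |
| 13% v 5% | 15-17% | 29-39% |
| 18% v 10% | 15-18% | 24-28% |
| 15% v 0% | 44-46% | 93-100% |

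**3. Where the gain shrinks or disappears.** These runs use three visits with within-patient correlation 0.6. Mann-Whitney counts as positive if p < 0.05 at any visit, which happens in 10-14% of runs with equal arms.
- Raised at all three visits, 18% v 10%: Mann-Whitney 27-29%, count 24-30%.
- A 10% general rise in Arm 1: 50-90% v 50-81% (8% v 0% affected) and 53-88% v 38-43% (13% v 5%).
- 40 per arm: 12-20% v 7-10% (8% v 0%) and 13-18% v 8-10% (13% v 5%).
- Median 1.0 UNL, 8% v 0%: the ≥ 2 UNL count has only 13-36%; a ≥ 3 UNL cut has 29-79%.

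**4. What an interval shows.** For 13/100 v 5/100 the Wilson limits are 0.0776 to 0.2098 and 0.0215 to 0.1118. Newcombe-Wilson then gives:
- lower: 0.08 − sqrt((0.13 − 0.0776)² + (0.1118 − 0.05)²) = −0.001
- upper: 0.08 + sqrt((0.2098 − 0.13)² + (0.05 − 0.0215)²) = 0.165

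The result is not significant (Fisher p = 0.08), yet an excess of up to about 16 points remains possible. At the interim size, 3/40 v 0/40 gives −2.5 to 19.9 points.

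**5. Unequal follow-up.** With no drug effect, median 1.0 UNL, log-SD 0.45 to 0.55 and half of Arm 2 missing two of three visits, a count over any visit shows a false Arm 1 excess of about 4 to 5 points. Fisher rejects in 8-13% of runs instead of about 3%. At median 0.6 UNL the false excess is 1 point or less.

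**The case against.** **The omission may lie in the extract.** The text is the synopsis of an interim report, and its paragraph on deviations refers to a final statistical analysis plan. Laboratory tables often sit there. This stands as a condition: if they exist, nothing is needed.

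**The outputs already planned cover part of the ground.** Adverse events are compared by arm and shown by severity, and the mean, SD and maximum are reported. A reader might infer from the low power that the plan hides extreme values or would miss liver injury altogether. The documents do not support that. In the single-measurement ALT model the required intervals for the two means fail to overlap in 87-98% of runs at 15% v 0% affected, but in only 12-19% at 13% v 5%. What remains missing is the number of patients per arm. Adverse event counts supply it only if the abnormality is recorded as an event. The supplied text gives no rule for that, and the trial is open-label, so the judgement is made knowing the arm.

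**The t-test may be kept.** It would have more power: about 46-92% at an 8-point excess in one assumed skewed model. But in the ALT model the normality check kept it in at most 0.1% of runs. With Gaussian values and a Kolmogorov-Smirnov check it can survive, with 21-31% power at 8 points.

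**The 16% comes from a chosen pattern, and counts do not always win.** Both statements stand, as step 3 shows. Nothing in the documents favours harm in a subset over a general shift.

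**Conclusion.** The point holds as a cheap improvement. In the supplied text, laboratory values are compared between arms only by a test at each visit, and no count beyond a limit is named. Power is low (7% to 45% for excesses of 3 to 15 points at 100 per arm) on three conditions: the test is Mann-Whitney at one visit, affected values lie above all others, and the remaining patients do not shift. The size of the excess and the absence of a shift are assumptions.

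A reader might take 16% as the power of this trial's laboratory comparisons in general, or conclude that counts would always detect more. Neither follows. A general rise in Arm 1 increases Mann-Whitney power well beyond that figure, and counts bring no power gain for 8-point excesses at the interim size. The lasting reason for the change is that counts with intervals show how many patients were affected and how large an excess is still compatible with the data.

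**What to change.** Keep the visit-wise test and add to the SAP, separately for each analyte and arm:

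- the number and share of patients with AST or ALT ≥ 2 UNL, total bilirubin ≥ 1.5 UNL, or creatinine clearance < 45 ml/min (the plan's own entry limits), plus AST or ALT ≥ 3 UNL (a suggested higher cut, not in the plan);
- the number tested at each visit;
- the difference in proportions with its 95% Newcombe-Wilson interval;
- shift tables from baseline to worst value.

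Make the main count per visit, or over Visits 2 and 3 among patients measured at them, since these are scheduled in both arms. Show Visit 4 and later separately, because Arm 2 can leave hospital early. An Arm 2 patient discharged before day 10 might also miss Visit 3, which is why the numbers tested must be shown.

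Treat the counts as descriptive, and at 40 per arm give counts and intervals only. State that a non-significant visit-wise p-value is not evidence of no laboratory harm.

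Cost: a few lines of SAP text and a few more safety tables, with no new patients, visits or samples on the footing that these values are already compared at the relevant visits (the laboratory schedule is not in the supplied text). The entry-limit counts will include some small crossings, which the ≥ 3 UNL cut helps to put in proportion for AST and ALT.

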2. OVERVIEW (SYNOPSIS)

Sponsor: PROMOMED RUS LLC, Russia	Separate study table relating to part of the dossier	(For use by national authorized bodies only)
Name of finished product: Areplivir, film-coated tablets	Volume: Pages:	
Active ingredient: Favipiravir		
Protocol No.: FAV052020		
Clinical study name: Open randomized multicenter comparative study on the efficacy and safety of Areplivir film-coated tablets (PROMOMED RUS LLC, Russia) in patients hospitalized with COVID-19		
Investigators, Study site: The study is conducted at five research centers in the Russian Federation. Detailed information is provided in Section 6.		
Publication: A list of scientific papers and publications relevant to this study will be presented in the Clinical Study Final Report.		
Study period: Q2 2020 – Q4 2020	Drug development phase: III	
Study purpose: Assess the efficacy and safety of Areplivir versus standard therapy in patients hospitalized with COVID-19. Study objectives: 
 • Assess the efficacy of Areplivir versus standard therapy in patients hospitalized with COVID-19. • Assess the safety of Areplivir versus standard therapy in patients hospitalized with COVID-19. 		
Methodology: an open randomized multicenter comparative study on the efficacy and safety of Areplivir in patients hospitalized with COVID-19.		
Number of patients (planned and included in the analysis): The study will randomize 200 patients. Given the possible non-inclusion of patients at the screening stage, the maximum number of patients to sign the Informed Consent Form in the Patient Information Leaflet and to participate in screening can be no more than 210 people. This interim report is based on data on 80 patients (40 patients in the Areplivir arm + 40 patients in the standard therapy arm). Patients who met the inclusion criteria and did not meet the non-inclusion criteria were randomized to 2 groups (treatment arms) in a 1:1 ratio: Arm 1 (n=100) receives the study drug Areplivir film-coated tablets: on day 1 of therapy - 1600 mg (8 tablets) 2 times a day; on days 2-14 of treatment - 600 mg (3 tablets) 2 times a day. The drug is taken orally every 12 hours, swallowing whole tablet without chewing and washing down with a glass of water. The course of treatment is 14 days.		

Sponsor: PROMOMED RUS LLC, Russia	Separate study table relating to part of the dossier	(For use by national authorized bodies only)

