In case change of the planned endpoints, separate adjustment will be made for the multiplicity of comparisons and the required number will be recalculated at the second stage.

The total planned number of patients before the completion of the first stage will be 100 patients in each of the arms.

The estimated calculation until the data of the first stage are obtained is as follows. Given the available data from Chinese researchers, 15% superiority of favipiravir therapy over standard therapy without favipiravir is allowed in relation to the rate of improvement by 2 or more categories on categorical scale by day 10 of treatment. The adopted higher response to standard therapy of 70% is associated with a longer duration relative to the Chinese study (10 days instead of 7 days).

An RCT enrolling patients within 12 days of symptom onset found that favipiravir was superior to arbidol in terms of the clinical recovery rate at day 7 in patients with mild illness (62 [56%] of 111 with arbidol vs 70 [71%] of 98 with favipiravir), but not in those with critical illness (0 vs 1 [6%]). (Chen C. Huang J. Cheng Z. et al. Favipiravir versus arbidol for COVID-19: a randomized clinical trial. medRxiv. 2020; (published online April 15.) (preprint).

Tests for Two Proportions

Numeric Results for Testing Two Proportions using the Z-Test with Unpooled Variance

H0: $P_1 - P_2 \geq 0$ vs. H1: $P_1 - P_2 = D_1 < 0$.

Target	Actual	Diff						
Power	Power*	N1	N2	N	P1	P2	D1	Alpha
0.80170	107	107	214	0.6500	0.8000	-0.1500	0.0500	0.80

* Power was computed using the normal approximation method.

Thus, the minimum number of subjects required for a clinical study is 200 with 100 subjects randomized to each of the two groups.

Statistical analysis

The purpose of statistical analysis is to prove superiority of Areplivir, film-coated tablets (PROMOMED RUS LLC, Russia), over standard therapy in patients hospitalized with COVID-19.

The results of statistical analysis, descriptive statistics and illustrative tables, graphs, lists will be presented in interim and final clinical study reports.

General methods of analysis

Statistical analysis is carried out in accordance with the requirements of the Guideline for Good Clinical Practice (ICH 9) approved by the Eurasian Economic Commission, and other applicable requirements and laws.

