
Sponsor: PROMOMED RUS LLC, Russia	Separate study table relating to part of the dossier	(For use by national authorized bodies only)
Name of finished product: Areplivir, film-coated tablets	Volume: Pages:	
Active ingredient: Favipiravir		

The proof of the superiority hypothesis is the establishment of a statistically significant time difference (in days) before patient's clinical status improvement between the Areplivir arm and the standard therapy arm.

The next primary efficacy parameter is the percentage of patients who achieved an improvement in clinical status according to the categorical ordinal scale of clinical improvement by 2 or more categories at Visit 3.

- Rate of clinical status improvement by categorical ordinal scale of clinical status improvement by 2 or more categories at Visit 3.

For the analysis of this parameter, an intergroup comparison of percentages is used using a two-sided version of the **Fischer's exact test** (or a two-sided version of the χ^2 (chi-square) test, if all the expected values in the cells of the contingency table for this analysis are 5 or more). The percentage of patients who achieved improvement in clinical status on a categorical ordinal clinical improvement scale by 2 or more categories at Visit 3 is presented with a two-sided 95% confidence interval by treatment arm. Hypothesis testing is performed at a 5% significance level. The difference in proportion between treatment arms and the 95% bilateral confidence interval for the difference in proportion calculated by **Newcomb-Wilson technique is presented**.

The proof of the hypothesis of superiority of Areplivir film-coated tablets (PROMOMED RUS LLC, Russia) is the establishment of a statistically significant difference in the proportions of patients who achieved an improvement in clinical status according to the categorical ordinal scale of clinical improvement by 2 or more categories at Visit 3, between Areplivir arm and standard therapy arm.

Analysis of the primary efficacy parameter is performed in the ITT population (main analysis), and in the PP population (additional analysis). A summary of all efficacy indicators is provided.

Analysis of secondary efficacy parameters

The following efficacy parameters in the protocol are represented by qualitative values:

- Percentage of patients with elimination * COVID-19 according to PCR analysis at Visit 3.
- Percentage of patients transferred to intensive care unit.

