
Said statistical power (45%) is acceptable for exploratory stages of the studies aimed to select the duration for endpoint monitoring and to select the endpoint at the second (confirming) stage. In case change of the planned endpoints, separate adjustment will be made for the multiplicity of comparisons and the required number will be recalculated at the second stage.
 
Significance level used in the clinical study Significance levels and confidence intervals are calculated as bilateral, the statistical significance of differences is two-sided by default and refers to significance level 0.05 (unless specified otherwise).
 
Stopping criteria for the clinical study This protocol does not contain any statistical criteria for stopping the clinical study.
 
Accounting for missing data, data not to be analyzed and questionable data In the case of for missing data, data not to be analyzed and questionable data, appropriate statistical analysis methods are applied. Patients who will not be able to complete the course of therapy according to the protocol are included in the analysis of the main endpoint using the last observation carried forward (LOCF) method. This means that measures taken as criteria for efficacy will be assessed for such patients at the time of dropping out of the study.
 
Procedures for reporting any deviations from the original statistical plan All deviations from the final version of the statistical analysis plan will be described and substantiated in the final clinical study report.
 
Population analysis The statistical analysis includes the following patient populations:
 
 Safety population: patients who have received at least one dose of the study drug and for whom there is an assessment of condition and/or AE for at least one time point after administration. Population of all patients included in the study (Intent-to-treat, ITT): patients who received at least one dose of the drug in the study and for whom there is data for at least one visit after the baseline (Visit 0). Population of patients who completed the study as per the Protocol (Per protocol, PP): patients who have completed the study as per the Study Protocol. 
In case of developing acute respiratory distress syndrome and the need to switch patient to mechanical ventilation, the investigational drug is canceled, but the patient is not withdrawn
									

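### The proof-of-superiority rules are not limited to the final analysis, so if a significant interim result counts as proof, the error for one endpoint is about 8.6% rather than 5%

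*Combined protocol and SAP*

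**What the plan says.** All references are to the synopsis (section 2) of the combined protocol and SAP.

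- **Where results go.** *Statistical analysis* gives proving superiority as the purpose of the analysis and says that results "will be presented in interim and final clinical study reports". Under *Number of patients*: "This interim report is based on data on 80 patients", 40 per arm.
- **The proof rule.** *Analysis of primary efficacy parameter* has one rule for each primary endpoint. For time to improvement: "The proof of the superiority hypothesis is the establishment of a statistically significant time difference (in days"). The rule for the response rate at Visit 3 has the same form. Neither names the analysis at which it applies.
- **The level.** *Significance level used in the clinical study*: "the statistical significance of differences is two-sided by default and refers to significance level 0.05 (unless specified otherwise"). For the response endpoint: "Hypothesis testing is performed at a 5% significance level". No different level is given for the interim.
- **Stopping.** "This protocol does not contain any statistical criteria for stopping the clinical study".
- **Multiplicity.** "In case change of the planned endpoints, separate adjustment will be made for the multiplicity of comparisons". This is the only adjustment promised.
- **Role of stage 1.** *Justification of sample size* and *Interim analysis* call the stage exploratory, aimed at choosing the endpoint and its observation period, and call stage 2 confirming. *Interim analysis* also gives the power to confirm a 15-point superiority with 40 per arm.
- **Final size.** "the minimum number of subjects required for a clinical study is 200 with 100 subjects randomized to each of the two groups".

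**The concern.** Read together, these passages let the same hypothesis be tested at the full two-sided 0.05 twice, on overlapping data, with either result meeting the written definition of proof. The authors of an interim report with p = 0.03 at 80 patients could call superiority proven without departing from the plan. If they did not, they would have a second chance at 200 patients with the level undiminished. The multiplicity sentence does not help when the endpoints stay as planned. Having no stopping rule does not help either, because a claim in an interim report does not require the trial to stop. What is at stake is whether the stated 5% describes the chance of a false superiority claim from this trial.

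**Working it through.** **Inputs.** Interim 80 patients and final 200, allocated 1:1 (*Number of patients*; *Justification of sample size*). Two-sided 0.05 at each look, critical value 1.96 (*Significance level*). Assumptions: the endpoint does not change; the 80 interim patients are part of the final 200 (no text excludes them); information is proportional to patients, so the fraction at the interim is 80/200 = 0.40.

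**The plan's own figure.** The stated interim power is 0.4553 for 65% against 80% with 40 per arm. Exact binomial enumeration of the pooled Z test at one-sided 0.05 gives 0.4553; at two-sided 0.05 it gives 0.32. The figure therefore reproduces only as a one-sided test. The plan's tests are two-sided, so two-sided 0.05 is used below.

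**Two looks, either one sufficing.** Under no difference, the interim and final statistics Z1 and Z2 are bivariate standard normal with correlation √0.40 = 0.632.

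- Error = 1 − P(|Z1| < 1.96 and |Z2| < 1.96) = 0.0863.
- Equivalently, 0.05 + 0.05 − P(both significant) = 0.0863, so P(both significant) = 0.0137.
- In the drug's favour only: 1 − P(Z1 < 1.96 and Z2 < 1.96) = 0.0432, against 0.025 for a single test.

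**Only the final test counts.** Error = P(|Z2| > 1.96) = 0.05. The earlier look does not change the distribution of Z2 when the trial continues regardless and the endpoint is unchanged.

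**Sensitivity.**

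| Variation | Two-sided error, either look counts |
|---|---|
| Final N 214 (the sample-size table's total), fraction 0.374 | 0.0871 |
| Fraction 0.40 | 0.0863 |
| Fraction 0.50 | 0.0831 |
| Simulated chi-square test, 40 then 100 per arm, common response 65% / 70% / 80% | 0.085 / 0.086 / 0.088 |

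**Levels that would hold 5% for one endpoint at fraction 0.40.** With interim p < 0.001 and the final left at 0.05, the error is 0.0504. To hold 0.05, the final critical value is 1.963, a two-sided level of 0.0496.

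**The case against.** The best reply is that the plan does give the stages different roles. Stage 1 is for selecting the endpoint and stage 2 is the confirming stage, and no sentence says that superiority will be concluded from 80 patients. The sentence about interim and final reports says where results appear, not where a claim is made. With no stopping rule, a trial that runs to 200 and tests an unchanged endpoint once keeps its 5% whatever was seen at 80.

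Much of this stands, and it makes the inflation conditional. A reader might infer that the 5% level is lost simply because an interim analysis exists. The documents do not support that. It is lost only if an interim p<0.05 is allowed to count as proof. But the exploratory label comes in a sentence explaining why 45% power is acceptable. It does not limit the proof rules or make interim p-values descriptive, and the interim section itself speaks of power to confirm superiority.

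A reader might also reach a larger figure, 13% to 17%, by letting either primary endpoint succeed at either look (assumed correlation 0.8 to 0; the documents give none). That does not measure the repeated look. The absence of an alpha split between two primary endpoints gives 7.8% to 9.8% at the final analysis alone over the same range. The larger figure also assumes that both endpoints go forward, whereas the plan intends to identify the more sensitive of the two at stage 1.

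**Conclusion.** The point holds in conditional form. As written, the plan permits a superiority claim at either look at two-sided 0.05, and it promises no adjustment unless the endpoints change. If significance at either look counts as proof, the two-sided error for one unchanged endpoint is about 8.6% instead of 5%, and 4.3% instead of 2.5% in the drug's favour. This assumes that the first 80 patients stay in the final test and that information is proportional to patients; varying the fraction from 0.374 to 0.50 moves the two-sided figure only between 8.7% and 8.3%. If only the final test counts, the interim look alone adds no error for an unchanged endpoint.

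The missing alpha split between the two primary endpoints and the choice of endpoint on stage 1 data are separate problems. Neither is in these figures, and settling this point does not settle them.

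**What to change.** In *Analysis of primary efficacy parameter* and *Interim analysis*, state that the proof-of-superiority rules apply only to the final analysis and that all interim between-arm p-values are descriptive, including in the interim report. This restriction only removes a chance to claim success, so it can be made even with the interim data in hand.

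An interim boundary is the alternative, for example p<0.001 at the interim with 0.0496 at the final, which gives 5.0% overall for one endpoint. It is valid only if fixed before the interim data are seen. The synopsis already describes an interim report based on the 80 patients, so that option may no longer be open. It also does not repair the two-endpoint problem: with interim 0.001 and final 0.05 applied to both endpoints, the error is still 7.8% to 9.8% (assumed correlation 0.8 to 0).

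The cost is a short addition to the text, with no extra patients or visits. The sponsor gives up claiming superiority at p<0.05 from the first 80 patients.
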